2.8.1.1 Adverse events of special interest / grouping of AEs

The number and percentage of patients with treatment emergent adverse events of special interest will be summarized for each type of event with a break-down for each type of event by SMQ (when applicable) and preferred term. The Compound Case Retrieval Strategy (CRS) will be used to determine the MedDRA search criteria to be used to identify events of special interest.

2.8.1.2 Adverse events reporting for safety disclosure

For the legal requirements of clinicaltrials.gov, two required tables on TEAEs which are not SAEs with an incidence greater than a certain threshold based on the final database and on treatment emergent serious adverse events and SAEs suspected to be related to study drug will be provided by system organ class and PT on the safety set population.

If for a same patient, several consecutive AEs (irrespective of study drug causality, seriousness and severity) occurred with the same SOC and PT:

- a single occurrence will be counted if there is ≤ 1 day gap between the end date of the preceding AE and the start date of the consecutive AE

- more than one occurrence will be counted if there is > 1 day gap between the end date of the preceding AE and the start date of the consecutive AE

For occurrence, the presence of at least one SAE / SAE suspected to be related to study treatment / non SAE has to be checked in a block e.g., among AE's in a ≤ 1 day gap block, if at least one SAE is occurring, then one occurrence is calculated for that SAE.

The number of deaths resulting from SAEs suspected to be related to study treatment and SAEs irrespective of study treatment relationship will be provided by SOC and PT.

2.8.2 Deaths

A summary of deaths will be presented by primary system organ class, preferred term, and treatment groups regardless of study drug relationship.

All the deaths in the clinical database including those occurring during screening will be listed, but only those between the first treatment and the last dose + 7 day will be included in summary tables. Additionally all deaths after first dose of study drug will be tabulated by treatment group.

2.8.3 Laboratory data

Laboratory data consist of hematology, biochemistry and urinalysis measurements.

Laboratory data measured after first intake of study drug and until 7 days after last intake of study drug are regarded as on-treatment data. Laboratory data measured more than 7 days after last intake of study drug are regarded as post-treatment data and will not be summarized. All data will be listed with abnormal values flagged.

2.8.3.1 Summary of absolute values

For all continuous laboratory parameters, the worst post-baseline values (including values from post-baseline unscheduled and premature discontinuation visits), will be summarized with standard descriptive statistics by parameter and treatment group.

The direction of interest for worst post-baseline for selected hematology and biochemistry parameters is tabulated in [Table 6.3.1](#). For continuous urinalysis parameters, the direction of interest is always High.

For categorical laboratory parameters and categorical urinalysis parameters, a frequency table of results will be produced by laboratory parameter and treatment. Worst post-baseline on-treatment values (including values from post-baseline unscheduled and premature discontinuation visits) will also be included.

For summary tables and figures on laboratory parameters considering values, which are lower or greater than the limit of quantification, the following approach will be taken. For values which are flagged as lower than the lower limit of quantification, the values presented in summary tables should be multiplied by 0.5 and for values which are flagged as greater than upper limit of quantification as 1.5, the values presented in summary tables should be multiplied by 1.5.

2.8.3.2 Summary of change from baseline

For continuous laboratory parameters, the on-treatment change from baseline to the worst post-baseline values (including values from post-baseline unscheduled and premature discontinuation visits) will be summarized by laboratory parameter and treatment group with standard descriptive statistics.

2.8.3.3 Notable values

For selected laboratory parameters, abnormalities occurring at any time-point over the on-treatment period, considering all post-baseline data from scheduled, unscheduled and premature discontinuation visits will be summarized.

The criteria for clinically notable values are presented in [Table 6.3.2](#).

Laboratory test units will be converted to standard units. Based on agreement within our standards, if we have a multi-region study the Blood Urea Nitrogen (BUN) / Urea test would be represented as BUN [mg/dL] for the regions used to conventional results (US, Latin America) and as Urea [mmol/L] for the regions used to SI (the international system of units) results. Therefore, both BUN and Urea parameters will be included in the data.

BUN is always reported as mg/dL and Urea as mmol/L. BUN and Urea are the same measurement in the lab and should be considered the same test. Hence, for the summary tables, it is expressed in SI units. Conversion to SI units includes the factor that incorporates a conversion from BUN to Urea as well as a conversion from mg/dL to mmol/L. This is necessary because BUN is Urea Nitrogen, not Urea and there are two nitrogens in each urea molecule. The factor of 0.357 converts BUN in mg/dL to Urea in mmol/L.

Listings of patients with notable laboratory values will be provided by laboratory parameter, treatment group, and patient number.

Additionally, box plot of change from baseline will be presented over time for ALT, AST, ALT/AST ratio, total bilirubin, creatinine, albumin, urine albumin, urine protein, urine albumin/creatinine ratio (ACR), urine protein/creatinine ratio (PCR). ACR value will be considered missing if either the albumin or the creatinine values are missing. Similarly, PCR will be considered missing if either the protein or the creatinine values are missing.

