All laboratory data will be listed by treatment group, subject, and visit and if normal ranges are available abnormalities will be flagged. Summary statistics will be provided by treatment group. Shift tables using the low/normal/high/ (low and high) classification will be used to compare baseline to the worst on-treatment value.

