This statistical analysis plan (SAP) describes all planned analyses for the Clinical Study Report (CSR) of study QAW039A2323, a 52-week phase IIIb, multicenter, randomized, double-blind, double-dummy, parallel-group, placebo-controlled study of fevipiprant once daily plus standard-of-care (SoC) for reduction of systemic corticosteroids (oral and parenteral) use in patients with severe asthma.

[figure not shown]
The content of this SAP is based on protocol QAW039A2323 version 01.

Data will be analyzed by Novartis or a contracted contract research organization (CRO) according to the data analysis section 9 of the study protocol which is available in [Appendix 16.1.1 of the CSR](#). Important information is given in the following sections and details will be provided, as applicable, in [Appendix 16.1.9 of the CSR](#).

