2.8.4 Other safety data

2.8.4.1 ECG and cardiac imaging data

ECG measurements include heart rate, QT interval, RR interval, PR interval, QRS duration, and Fridericia's QTc (calculated as $QTcF = QT / 3\sqrt{RR}$ (in seconds), where $3\sqrt{}$ denotes the cube root).

ECG data measured more than 1 day after last intake of study drug are regarded as post treatment data and will not be summarized. All data will be included in the analyses regardless of rescue medication use.

Clinically relevant values

- The number and percentage of patients with newly occurring or worsening clinical relevant QTcF values (see [Table 2.8.1](#)) summarized at any time on treatment considering all post-baseline data from scheduled, unscheduled and premature discontinuation visits.

Table 2.8.1 Clinically relevant criteria for QTcF (Fridericia's formula)

ECG parameter (unit)	Clinically relevant range
Value considering newly occurring or worsening cases	
QTc (msec)	≥ 450 (male)
QTc (msec)	≥ 460 (female)
QTc (msec)	> 500 (both)
Change from baseline	
QTc	< 30
QTc	30 – 60
QTc	> 60

Clinically notable values

- A summary table will also be produced for number and percentage of subjects with notable QT and QTcF intervals (irrespective of the time point) using the following categories:
 - any treatment emergent (new) QTcF or QT interval ≥ 450 ms – 480 ms, > 480 ms – 500 ms or > 500 ms
 - QTcF or QT increase from baseline of ≥ 30 ms – < 60 ms, ≥ 60 ms
 - QTcF and QT increase from baseline of ≥ 30 ms plus QTcF interval ≥ 450 ms, > 480 ms or > 500 ms
 - QTcF increase from baseline of ≥ 60 ms plus QTcF interval ≥ 450 ms, > 480 ms or > 500 ms
- The number and percentage of subjects with noteworthy PR, QRS and HR interval changes will be reported using the below categories:
 - New PR > 200 ms to ≤ 220 ms; and > 220 ms
 - New QRS > 110 ms to ≤ 120 ms; and > 120 ms
 - PR increase $> 25\%$ to a value > 200 ms
 - QRS increase $> 25\%$ to a value > 120 ms
 - HR decrease $> 25\%$ to a HR < 50 bpm
 - HR increase $> 25\%$ to a HR > 100 bpm

Patients with notable post-baseline ECG values will be listed.

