2.8.4.2 Vital signs

Vital signs measurements include systolic and diastolic blood pressure (SBP and DBP), pulse rate, temperature, height and body weight. Vital signs data taken on or after the time of the first intake of study drug and until 7 days after the last intake of study drug are regarded as on-

treatment data. Vital signs data measured more than 7 days after last intake of study drug are regarded as post-treatment data and will not be summarized. All data will be included in the analyses regardless of rescue medication use.

The following analyses will be performed by treatment group:

- absolute on-treatment values and change from baseline summarized by parameter, and treatment group
- the number and percentage of patients with newly occurring or worsening notable vital signs on-treatment values (see [Table 2.8.2](#) for definition of notable values) summarized by parameter (except height), at any time on treatment considering all post-baseline data from scheduled, unscheduled and premature discontinuation visits
- Vital signs will also be summarized by clinically relevant categories:
 1. Pulse rate: < 40 bpm, 40 – 90 bpm, and > 90 bpm
 2. Systolic blood pressure: < 90 mm Hg, 90 – 140 mm Hg, and > 140 mm Hg
 3. Diastolic blood pressure: < 50 mm Hg, 50 – 90 mm Hg, and > 90 mm Hg.

The same approach as for notable laboratory values will be used to define a newly occurring notable vital sign value and a worsening notable vital sign value.

A listing of all patients with notable vital sign values and changes will be provided.

Table 2.8.2 Clinical notable criteria for vital signs

Vital sign parameter (unit)	Lower bound of clinically notable range	Upper bound of clinically notable range
Notable value considering newly occurring or worsening cases		
Systolic blood pressure (mmHg)	< 75	> 200
Diastolic blood pressure (mmHg)	< 40	> 115
Pulse rate (bpm)	< 40	> 130
Notable change from baseline		
Systolic blood pressure (mmHg)	≤ 90 and decrease from baseline by ≥ 20	≥ 180 and increase from baseline by ≥ 20
Diastolic blood pressure (mmHg)	≤ 50 and decrease from baseline by ≥ 15	≥ 105 and increase from baseline by ≥ 15
Pulse rate (bpm)	≤ 50 and decrease from baseline by ≥ 15	≥ 120 and increase from baseline by ≥ 15
Weight (kg)	Decrease ≥ 7% from baseline	Increase ≥ 7% from baseline

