t is the randomization ratio

p_c are the % of patients in category c for the experiment arm

q_c are the % of patients in category c for the control arm

D is number of categories

4 Change to protocol specified analyses

The primary endpoint will be analyzed as specified in the protocol for the CSR and is detailed in this SAP. As the study is terminated early by sponsor, most of the patients don't have sufficient follow up and most of the data will not be matured enough do the analysis as defined in the protocol, due to that all secondary endpoints will be analyzed descriptively.

NA

5 Appendix

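### SAP 2.8.3.3 counts notable laboratory values with no baseline condition, and the protocol's baseline-to-worst shift tables are missing from the SAP without being declared as a change

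*SAP*

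**What the plan says.** **Laboratory values.** For a chosen set of tests, SAP 2.8.3.3 states that "abnormalities occurring at any time-point over the on-treatment period, considering all post-baseline data from scheduled, unscheduled and premature discontinuation visits will be summarized". Cut-offs are set in SAP Table 6.3.2, which gives absolute low and high bounds only.

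**ECG and vital signs.** SAP 2.8.4.1 counts "newly occurring or worsening clinical relevant QTcF values", and SAP 2.8.4.2 counts "newly occurring or worsening notable vital signs on-treatment values". Tables 2.8.1 and 2.8.2 carry the same condition in their row headings. SAP 2.8.4.2 also plans a second vital-signs summary by broad categories, which has no baseline condition.

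**Cross-reference.** For vital signs, SAP 2.8.4.2 says: "The same approach as for notable laboratory values will be used to define a newly occurring notable vital sign value", and likewise for a worsening value.

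**Protocol.** Section 9.5.2, under clinical laboratory evaluations, says: "Shift tables using the low/normal/high/ (low and high) classification will be used to compare baseline to the worst on-treatment value". SAP 2.8.3.1 to 2.8.3.3 contain no shift table.

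**Scope and declared changes.** SAP 1 says the document covers every analysis planned for the study report. It also says data will be analysed "according to the data analysis section 9 of the study protocol". SAP 4 attributes its one departure to early termination: "due to that all secondary endpoints will be analyzed descriptively".

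**The concern.** A count of patients with a notable value at any on-treatment visit mixes two groups: those who became notable on treatment, and those who were already notable and stayed so. Randomisation puts the second group in all arms in roughly equal proportion. It therefore adds a similar background to each count and pulls the ratio between arms towards 1. A baseline-to-worst shift table would separate the two groups. The protocol promises one, and the SAP does not specify it.

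The vital-signs count is affected too. Its definition of new and worsening points to a laboratory rule that is not written down, so two programmers could produce different tables from the same text.

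**Working it through.** The documents give no figure on this point, so there is none to reproduce. The check has three parts.

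**1. Is a baseline condition stated for laboratory values?** SAP 2.8.3.1 covers worst post-baseline values, and frequency tables for categorical parameters. SAP 2.8.3.2 covers change from baseline to the worst value, for continuous parameters. SAP 2.8.3.3 covers notable values. None of these, nor Table 6.3.2, defines newly occurring or worsening, so the reference in SAP 2.8.4.2 leads nowhere.

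**2. Can an enrolled patient be notable at baseline?** Compare Protocol 4.2 with SAP Table 6.3.2:

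| Parameter | Entry limit (Protocol 4.2) | Notable bound (SAP Table 6.3.2) | Notable baseline possible? |
|---|---|---|---|
| ALT, AST | excluded above 2 x ULN at run-in | 3 x ULN | largely ruled out |
| White cells | excluded below 2500/µL (2.5 x10^9/L) | low bound 2.8 x10^9/L | yes, 2.5 to 2.8 |
| CPK | excluded above 2 x ULN, statin users only | 4 x ULN | yes, without a statin |
| Haemoglobin, haematocrit, platelets, gamma-GT | no numeric limit | absolute bounds | yes |
| Dipstick blood, glucose, leukocytes, protein | no numeric limit | 2+ or more | yes |

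Exclusion 17 also lets the investigator exclude other clinically significant laboratory abnormalities, so the last column shows what the numeric limits allow, not what will be common.

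**3. How much would the count be diluted?** Let b be the proportion notable at baseline, equal across arms and persisting on treatment. Let i be the new-onset rate among the rest. The proportion counted under SAP 2.8.3.3 is

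P = b + (1 - b) x i.

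Assume i = 2% in one arm and 6% in the other. All rates here are assumptions.

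| b | Lower arm | Higher arm | Ratio | Difference |
|---|---|---|---|---|
| 0% | 2.0% | 6.0% | 3.00 | 4.0 points |
| 2% | 0.02 + 0.98 x 0.02 = 4.0% | 0.02 + 0.98 x 0.06 = 7.9% | 1.99 | 3.9 points |
| 5% | 0.05 + 0.95 x 0.02 = 6.9% | 0.05 + 0.95 x 0.06 = 10.7% | 1.55 | 3.8 points |
| 10% | 0.10 + 0.90 x 0.02 = 11.8% | 0.10 + 0.90 x 0.06 = 15.4% | 1.31 | 3.6 points |

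Restricting the count to patients who are not notable at baseline gives (1 - b)i / (1 - b) = i in each arm, so the ratio returns to 3.00 for any b.

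**A trap in the remedy.** Protocol Table 6-1 schedules laboratory tests at seven post-baseline clinic visits (weeks 6, 12, 20, 28, 36, 44 and 52). Suppose a baseline-notable patient's continuous values merely fluctuate, so that the baseline and the seven later values are exchangeable. The chance that at least one later value is more extreme than baseline is then 7/8, or about 88%. Counting any value further outside the bound as worsening would bring most of these patients back in.

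**The case against.** The strongest reply is that the SAP does intend a baseline condition. SAP 2.8.4.2 would not borrow a laboratory definition of new and worsening unless the authors thought one existed, and SAP 1 also defers to Protocol section 9, which contains the shift tables. This stands to a degree. It rules out reading SAP 2.8.3.3 as a deliberate choice to count pre-existing abnormalities, and it rules out saying the shift tables were removed. It does not supply the missing rule. Nor does SAP 4 explain the absence of the tables: its reason is that secondary endpoints become descriptive, and shift tables are already descriptive.

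The second reply is that little is lost. The SAP plans no test or ratio for laboratory counts. Change from baseline to the worst value is kept for continuous parameters. Box plots of change cover ALT, AST, bilirubin, creatinine, albumin and the urine albumin and protein measures. All values are listed with abnormal ones flagged, and Protocol 7.1 makes clinically significant laboratory abnormalities adverse events. Exclusion 17 is open-ended, and diabetes and hepatic disease are excluded. All of this stands and keeps the point small. What it does not cover is a change of category from baseline. Categorical urinalysis gets frequency tables only, so dipstick results have no baseline-referenced summary. The quantitative urine box plots are a partial substitute for dipstick protein alone.

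**Conclusion.** The point holds in a limited form, and it is minor. SAP 2.8.3.3 states no baseline condition, the definition that SAP 2.8.4.2 relies on is missing, and the shift tables of Protocol 9.5.2 are omitted without being declared. Followed literally, the plan counts pre-existing notable values as on-treatment for white cells between 2.5 and 2.8 x10^9/L, haemoglobin, haematocrit, platelets, gamma-GT, CPK without a statin, and dipstick results, subject to exclusion 17.

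Under the assumed rates, a ratio of 3.00 falls to between 1.99 and 1.31 for a baseline prevalence of 2% to 10%. This rests on that prevalence being equal across arms and persisting on treatment; the documents give no prevalence.

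A reader might infer that laboratory safety signals in general are masked. The documents do not support that: the absolute difference barely moves (4.0 to 3.6 points), the ALT and AST entry limit lies below the notable bound, and continuous change from baseline is still reported. The primary analysis is not affected.

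**What to change.** 1. In SAP 2.8.3.3, make newly occurring notable values the main count: not notable at baseline in that direction, and notable at least once on treatment. The denominator is patients with a non-notable baseline value and at least one post-baseline value.
2. Report worsening from a notable baseline on a separate line, with a margin or category step stated in advance, so that ordinary fluctuation is not counted.
3. Apply the same definitions in SAP 2.8.4.2, so that its cross-reference has a target.
4. Reinstate the baseline-to-worst shift tables of Protocol 9.5.2 in SAP 2.8.3, including categorical urinalysis.

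The cost is SAP wording and standard tables, with no new data collection. Patients without a baseline value leave the denominator, and their number should be shown.

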2.8.4 Other safety data

2.8.4.1 ECG and cardiac imaging data

ECG measurements include heart rate, QT interval, RR interval, PR interval, QRS duration, and Fridericia's QTc (calculated as $QTcF = QT / 3\sqrt{RR}$ (in seconds), where $3\sqrt{}$ denotes the cube root).

ECG data measured more than 1 day after last intake of study drug are regarded as post treatment data and will not be summarized. All data will be included in the analyses regardless of rescue medication use.

Clinically relevant values

- The number and percentage of patients with newly occurring or worsening clinical relevant QTcF values (see [Table 2.8.1](#)) summarized at any time on treatment considering all post-baseline data from scheduled, unscheduled and premature discontinuation visits.

Table 2.8.1 Clinically relevant criteria for QTcF (Fridericia's formula)

ECG parameter (unit)	Clinically relevant range
Value considering newly occurring or worsening cases	
QTc (msec)	≥ 450 (male)
QTc (msec)	≥ 460 (female)
QTc (msec)	> 500 (both)
Change from baseline	
QTc	< 30
QTc	30 – 60
QTc	> 60

Clinically notable values

- A summary table will also be produced for number and percentage of subjects with notable QT and QTcF intervals (irrespective of the time point) using the following categories:
 - any treatment emergent (new) QTcF or QT interval ≥ 450 ms – 480 ms, > 480 ms – 500 ms or > 500 ms
 - QTcF or QT increase from baseline of ≥ 30 ms – < 60 ms, ≥ 60 ms
 - QTcF and QT increase from baseline of ≥ 30 ms plus QTcF interval ≥ 450 ms, > 480 ms or > 500 ms
 - QTcF increase from baseline of ≥ 60 ms plus QTcF interval ≥ 450 ms, > 480 ms or > 500 ms
- The number and percentage of subjects with noteworthy PR, QRS and HR interval changes will be reported using the below categories:
 - New PR > 200 ms to ≤ 220 ms; and > 220 ms
 - New QRS > 110 ms to ≤ 120 ms; and > 120 ms
 - PR increase $> 25\%$ to a value > 200 ms
 - QRS increase $> 25\%$ to a value > 120 ms
 - HR decrease $> 25\%$ to a HR < 50 bpm
 - HR increase $> 25\%$ to a HR > 100 bpm

Patients with notable post-baseline ECG values will be listed.

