5.6.2 Discontinuation of study treatment

Discontinuation of study treatment for a subject occurs when study treatment is stopped earlier than the protocol planned duration, and can be initiated by either the subject or the investigator.

The investigator must discontinue study treatment for a given subject if, he/she believes that continuation would negatively impact the subject's well-being.

Study treatment must be discontinued under the following circumstances:

- Withdrawal of informed consent (and the investigator must prematurely withdraw the patient from the study);
- Pregnancy;
- Female subjects non-compliant with the chosen effective method of contraception during the study: The investigator must provide appropriate advice on the continued use of effective contraception for at least one week (at least 5 half-lives of QAW039) after study drug discontinuation and follow up with the subject as appropriate at least to the end of this period;
- Any protocol deviation that results in a significant risk to the patient's safety;
- Liver laboratory test abnormality / event (see [Section 14](#)):
 - Abnormal liver laboratory results requiring discontinuation – refer to [Table 14-2 - Appendix 2](#);
- If the investigator considers it appropriate after the confirmation of a liver safety monitoring signal:

- ALT or AST $\geq 2.5 \times$ ULN **and** total bilirubin $\geq 1.5 \times$ ULN ([Section 14](#));
- Any laboratory abnormalities that in the judgment of the investigator, taking into consideration the subject's overall status, prevents the subject from continuing participation in the study;
- Premature unblinding of study treatment for a patient for any reason; please refer to [Section 5.5.9](#);
- Total white blood cell count < 1000 cells/ μ L;
- If patients on statin therapy complain of persistent muscle pain without any obvious cause for greater than 3 days accompanied by increase in CK levels $> 10 \times$ ULN or persistent intolerable muscle pain regardless of the accompanying CK level;
- If a patient develops a medical condition that requires consistent use of prohibited treatment as per [Section 5.5.8](#) or if patient exhibits a behavior of non-compliance regarding prohibited medication.

If discontinuation of study treatment occurs, the investigator should make a reasonable effort to understand the primary reason for the subject's premature discontinuation of study treatment and record this information.

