9.5.2 Safety variables

For all safety analyses, the safety set will be used. All listings and tables will be presented by treatment group.

Safety summaries (tables, figures) include only data from the on-treatment period with the exception of baseline data which will also be summarized where appropriate (e.g. change from baseline summaries). In addition, a separate summary for death including on treatment and post treatment deaths will be provided. In particular, summary tables for adverse events (AEs) will summarize only on-treatment events, with a start date during the on-treatment period (treatment-emergent AEs).

The on-treatment period lasts from the date of first administration of study treatment to 14 days after the date of the last actual administration of any study treatment.

Adverse events

All information obtained on adverse events will be displayed by treatment group and subject.

The number (and percentage) of subjects with treatment emergent adverse events (events started after the first dose of study medication or events present prior to start of double-blind treatment but increased in severity based on preferred term) will be summarized in the following ways:

- by treatment, primary system organ class and preferred term.
- by treatment, primary system organ class, preferred term and maximum severity.
- by treatment, Standardized MedDRA Query (SMQ) and preferred term

Separate summaries will be provided for study medication related adverse events, death, serious adverse events, other significant adverse events leading to discontinuation and adverse events leading to dose adjustment.

The adverse events of special interest will be listed and summarized by treatment group.

A subject with multiple adverse events within a primary system organ class is only counted once towards the total of the primary system organ class.

Vital signs

All vital signs data will be listed by treatment group, subject, and visit and if ranges are available, abnormalities will be flagged. Summary statistics will be provided by treatment group.

12-lead ECG

All ECG data will be listed by treatment group, subject and visit, abnormalities will be flagged. Summary statistics will be provided by treatment.

Clinical laboratory evaluations

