ACQ-5	Baseline ACQ-5 score is defined as ACQ-5 scores obtained on Day 1. If the ACQ-5 score on Day 1 is missing then the last available ACQ-5 score prior to Day 1 will be used. If the ACQ-5 score is missing on Day 1 and on all visits before Day 1, the respective baseline value will be set to missing.	ACQ assessments are taken during screening and on day 1.
e-Diary daytime and night time asthma symptoms	For e-diary data (daytime and night time asthma symptoms) which are collected daily, the mean score for the baseline is calculated from Visit 101 to Day 1) will be considered as the baseline mean score. The non-missing data within that interval will be used to calculate the mean value	Note that the morning assessment for Day 1 counts towards the baseline (as a part of run-in). However, the evening assessment for Day 1 counts as the treatment period (not as a part of run-in).

	
as long as there are at least 75% days in the period with non-missing e-diary data. Since these measurements are collected at both morning and evening at Day 1, the morning assessment for Day 1 counts towards the baseline (as a part of run-in) while the evening assessment counts as the treatment period.
	
--	---	--

Post-baseline measurement

Post baseline measurements are defined as those assessments after the start of study treatment.

Change from baseline

When change from baseline is of interest, the following formula will be used for each scheduled visit and time-point where baseline and post-baseline values are both available:

Change from baseline = post-baseline value – baseline value; and

If baseline or post-baseline values are missing, then the change from baseline will be missing.

On-treatment assessment/event and observation periods

The overall observation period will be divided into three mutually exclusive segments:

1. **pre-treatment period:** from day of patient’s informed consent to the day before first administration of study treatment
2. **on-treatment period:** from date of first administration of study treatment to date of last actual administration of any study treatment (including start and stop date)
3. **post-treatment period:** starting at day 1 after last administration of study treatment.

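### The SAP's 1-day cut-off for ECG summaries departs from the protocol's 14-day safety window without declaring it, and may exclude some patients' only scheduled post-baseline ECG

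*SAP*

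**What the plan says.** **ECG rule.** SAP 2.8.4.1: "ECG data measured more than 1 day after last intake of study drug are regarded as post treatment data and will not be summarized".

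**Protocol window.** Protocol 9.5.2 restricts safety summaries to on-treatment data, apart from baseline values and a separate summary of deaths. It defines the period as running "to 14 days after the date of the last actual administration of any study treatment". ECG is among the data covered. The SAP introduction says analysis will follow section 9 of the protocol.

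**Other SAP windows.** For laboratory data, SAP 2.8.3 says: "Laboratory data measured more than 7 days after last intake of study drug are regarded as post-treatment data and will not be summarized". For vital signs, SAP 2.8.4.2 says: "Vital signs data measured more than 7 days after last intake of study drug are regarded as post-treatment data". SAP 2.8.1 and 2.8.2 also use 7 days, for treatment-emergent adverse events and for the main death table. The general definition in SAP 2.1.1 is shorter than any of these, with the post-treatment period "starting at day 1 after last administration of study treatment".

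**Schedule.** Protocol Table 6-1 marks ECG twice, at Screening and once at the end. SAP 2.1.1 takes the screening ECG as baseline.

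**Termination.** SAP section 4 begins its explanation with "As the study is terminated early by sponsor" and reports that secondary endpoints will be analysed descriptively. It says nothing about safety windows.

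**The concern.** One assessment is summarised over a much shorter period than the protocol set, with no reason given and no entry among the declared changes. That is a defect however many records it touches.

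The short window also falls on the assessment that can least absorb it. Laboratory tests and vital signs are repeated at the clinic visits, so losing a late value usually leaves earlier ones. ECG has one scheduled post-baseline record per patient. If that record falls outside the window, nothing scheduled remains in the tables for that patient.

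The exclusion need not be random. Protocol 6.3 has patients take a dose from their returned medication at the end-of-treatment visit, so the ECG of a patient still on drug falls on the last-dose day and is kept. The ECG at risk belongs to a patient who stopped drug first and attended later. Early termination makes that situation more likely to arise.

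ECG is a named component of the safety objective (Protocol Table 2-1). Protocol 3.6 lists increased heart rate and palpitations as potential effects and relies partly on ECG to monitor cardiovascular risk.

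**Working it through.** The plan states no figure to reproduce, because this is a question of data windows. The check has four steps.

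**1. Windows side by side**

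| Source | Data | Days after last dose still summarised |
|---|---|---|
| Protocol 9.5.2 | all safety data | 14 |
| SAP 2.8.1, 2.8.2, 2.8.3, 2.8.4.2 | adverse events, deaths, laboratory, vital signs | 7 |
| SAP 2.8.4.1 | ECG | 1 |
| SAP 2.1.1 | general definition | 0 |

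There are four different windows. SAP section 4 declares none of the departures from 14.

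SAP 2.8.4.1 also sits uneasily with itself. Its QTcF summary is to draw on scheduled, unscheduled and premature-discontinuation visits, but only while on treatment. The 1-day rule can then remove the very discontinuation-visit ECGs that the sentence names.

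**2. Scheduled ECGs per patient**

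Two marks, less one used as baseline, leave 1 scheduled post-baseline ECG. The column of the second mark is uncertain: in the text as read it lines up with the Day 378 telephone contact. HbA1c has the same alignment, and Protocol 6.5.5.2 places HbA1c at end of treatment, so I take the ECG mark as end of treatment or discontinuation. The argument needs only that there is a single end mark.

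**3. Share of these ECGs kept (illustration on an assumed lag)**

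Protocol 5.6.5 leaves open when patients stop drug and when they attend after a termination, so the lag is unknown. Assume it is uniform over 0, 1, ..., L whole days. For a window of w days, share kept = (min(w, L) + 1) / (L + 1).

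| L (days) | w = 1 (SAP ECG) | w = 7 (other SAP safety data) | w = 14 (protocol) |
|---|---|---|---|
| 0 or 1 | 100% | 100% | 100% |
| 3 | 2/4 = 50% | 100% | 100% |
| 7 | 2/8 = 25% | 8/8 = 100% | 100% |
| 14 | 2/15 = 13% | 8/15 = 53% | 15/15 = 100% |
| 28 | 2/29 = 7% | 8/29 = 28% | 15/29 = 52% |

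Under the 1-day rule the share lost runs from 0% to 93%, depending wholly on L. This is a sensitivity range, not an estimate.

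**4. Drug still present**

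Protocol 5.6.2, on contraception after stopping drug, gives the period as "at least one week (at least 5 half-lives of QAW039". If 168 h covers at least 5 half-lives, the half-life is at most 168/5 = 33.6 h. Assuming simple exponential decline, the largest fractions that could remain are:

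- 48 h: 2^(-48/33.6) = 0.37
- 7 days: 2^(-168/33.6) = 2^(-5) = 0.031
- 14 days: 2^(-336/33.6) = 2^(-10) = 0.001

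These are upper bounds. An ECG on the second day may still be taken with appreciable drug present. One taken towards day 7 is nearly drug-free, and one at day 14 essentially so.

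**The case against.** **The records are not discarded.** This stands. SAP 2.1.1 lists all safety data and flags those from the post-treatment period, SAP 2.8.4.1 lists patients with notable post-baseline ECG values, and Protocol 9.5.2 lists all ECG data. A late abnormal ECG stays visible. What is lost is its place in the by-arm counts, which a listing does not replace.

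**Wider tables may cover it.** SAP 2.8 promises selected tables on all data after the first dose. ECG is not named there, so this leaves room for a fix but does not commit to one.

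**ECG is not treated worse than the SAP's own default.** This also stands. The general definition is 0 days, and SAP 2.7.2 uses last dose + 1 for secondary endpoints. The accurate criticism is that several windows are unreconciled, not that ECG alone was narrowed.

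**A short window is defensible for ECG.** Intervals can follow drug concentration, 1 day is one dosing interval for a once-daily drug, and later ECGs could dilute a QTc signal. This is a fair reason to keep a 1-day table. It does not explain why the protocol's window was replaced without saying so.

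**Other routes exist.** Protocol 6.5.6 calls for repeat ECGs when there is a safety concern, so the end ECG is the only *scheduled* post-baseline one, not necessarily the only one. Cardiac events that led to stopping drug also appear in the adverse event tables to day 7.

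**Conclusion.** The inconsistency is established: 1 day in SAP 2.8.4.1 against 14 days in Protocol 9.5.2, 7 days for the SAP's other safety data and 0 days in its general definition, with no declaration in SAP section 4. It is also established that the rule can remove a patient's only scheduled post-baseline ECG from the summaries, and that this would fall on patients who stopped drug before the visit rather than on those who dosed at it.

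A reader might infer that much of the trial's post-baseline ECG evidence goes unsummarised because the trial was stopped early. The documents do not support that. They give neither the interval from last dose to final visit nor how patients were brought in at termination. If patients dosed until the final visit or the day before it, the loss is nil.

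The conclusion assumes that the single end mark in Table 6-1 means end of treatment or discontinuation. The half-life bound supports the choice of a longer window but is not needed to show the inconsistency. The point is worth correcting because the ECG tables could be selectively incomplete and the correction is small. It does not show that a cardiac signal would be missed.

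**What to change.** 1. In SAP 2.8.4.1, summarise ECGs over the protocol's 14-day on-treatment window. Alternatively, use the SAP's own 7-day window and declare that departure from the protocol in SAP section 4.
2. Reword SAP 2.8.4.1 so that the window and the inclusion of premature-discontinuation visits agree, and reconcile both with the general definition in SAP 2.1.1.
3. Add days since last dose to the ECG listing.
4. Report by arm how many patients have a post-baseline ECG outside the chosen window, and how many have none inside it.
5. Keep the 1-day summary as a supplementary table for ECGs taken close to dosing.

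The cost is one number, a sentence or two in the SAP, one listing column and a short count table, with no new data collection. The downside is that some ECGs taken at reduced exposure enter the main table, more so with 14 days than with 7. The supplementary table and the days-since-dose column let a reader judge that dilution.
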